12.5.2 General Behavior Inventory (GBI) 10-Item Mania Scale

The GBI 10-item mania scale is a parent- and patient-rated scale designed to screen for manic symptoms in children and adolescents. The ten items are rated on a 4-point scale from 0 (never or hardly ever) to 3 (very often or almost constantly). The total score ranges from 0 to 30, with higher scores indicating greater pathology. Only the parent-rated scale will be used in this study.

Summary statistics on the total score, absolute scores as well as changes from baseline for each visit as well as the latest assessment will be presented per study period and inclusion source (Open Label Period) and treatment group (Double-Blind Treatment Period).

13 Interim Analyses

No interim analyses will be performed.

14 Sample Size Considerations

The calculation of power is based on a log-rank test for the time to relapse at a one-sided 5% level of significance using SAS Proc Power. A sample size of 80 randomized patients (40 patients per treatment group) will provide at least 80% power to find a difference between vortioxetine and placebo as statistically significant, when expecting cumulative relapse rates at 0.42 and 0.69 over 26 weeks, respectively corresponding to a hazard-ratio of 2.15. The assumption of relapse rates (42% and 69% over 6 months for vortioxetine and placebo, respectively) is based on observed rates from a similarly designed relapse-prevention study of fluoxetine in pediatric patients with MDD who had an adequate response after 12 weeks of acute treatment¹.

It is anticipated that approximately 60% of *de novo* patients enrolled into the Open Label Period will qualify for the Double-Blind Treatment Period. To achieve 80 randomized patients, 150 patients are estimated to be enrolled into the study (depending on number and randomization rate of *de novo* and rollover patients).

15 Statistical Software

The statistical software used will be SAS[®], Version 9.4 or later.

16 Details on Data Handling

An LOCF approach will be used for the Double-Blind Treatment Period of the following scales: CDRS-R, PQ-LES-Q, CGI-I and CGI-S.

The LOCF approach will only be used for the total scores (if applicable). The last usable assessment in the Double-Blind Treatment Period (excluding the randomization assessment) will be used to impute missing values for the LOCF. See also section [Section 16.1.3](#) for the handling of missing data related to COVID-19.

16.1 Assigning Data to Visits

16.1.1 Visit Window

The assessments at the scheduled visits will be used for the analyses. The assessment at the Withdrawal Visit for patients withdrawn from study will be assigned to a nominal visit in the Treatment Period, according to the visit windowing specified in [Panel 6](#). If the assessment at the Withdrawal Visit is assigned to the same visit as an assessment at a scheduled visit, the assessment from the Withdrawal Visit, which by definition always will be the latest, will be used.

Panel 6 Visit Windows

Nominal Visit Number	Nominal Visit Week	Nominal Visit Week (relative to randomization)	Nominal Visit Day	Time Window (days)	Mapping Window (days)
Open Label Period					
V1(screen)			-15	-5 to -15	
V2(baseline)	0	NA	0	-	
V3	1	NA	7	4 to 10	1 to 10
V4	2	NA	14	11 to 17	11 to 21
V5	4	NA	28	25 to 31	22 to 42
V6	8	NA	56	53 to 59	43 to 63
V7	10	NA	70	67 to 73	64 to 77
V8(end of Open Label Period)	12	NA	84	81 to 87	78 to 86
Safety follow-up (end of Open Label, for patients not entering Double-Blind Treatment Period)	16	NA	112	110 to 114	>86
Double-Blind Treatment Period					
V8(baseline of Double-Blind Treatment Period)	12	0	84	81 to 87	78 to 86
V9	13	1	91	88 to 93	87 to 95
V10	14	2	98	95 to 101	96 to 105
V11	16	4	112	107 to 117	106 to 119
V11, CGI-I only*	16	4	112	107 to 117	101 to 133
V12	18	6	126	121 to 131	120 to 140
V13	22	10	154	149 to 159	141 to 168
V13, CGI-I and PQ-LES-Q only*	22	10	154	149 to 159	134 to 182
V14	26	14	182	177 to 187	169 to 196
V15	30	18	210	205 to 215	197 to 224
V15, CGI-I and PQ-LES-Q only*	30	18	210	205 to 215	183 to 238
V16	34	22	238	233 to 243	225 to 252
V17	38	26	266	261 to 271	253 to 280
V18 - Safety follow-up (end of Double-Blind Treatment Period, for patients who completed the Double-Blind Treatment Period)	42	30	294	289 to 299	>281

*Different mapping for these variables only, due to a different schedule of assessments

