AE = adverse event; CDRS-R = Children depression rating scale revised version; CGI-S = Clinical Global Impression – Severity of Illness; C-SSRS = Columbia-Suicide Severity Rating Scale; ECG = electrocardiogram; eCRF = electronic case report form; GBI= General Behaviour Inventory; IMP = investigational medicinal product; K-SADS-PL = The Kiddie-Schedule for Affective Disorders and Schizophrenia for School-aged Children, Present and Lifetime version; PQ-LES-Q = Pediatric Quality of Life Enjoyment and Satisfaction Questionnaire – Patient rated; SAE = serious AE

- a Screening visit will be performed only for *de novo* patients. Patients rolling over from Study 12709A will proceed directly to the Baseline Visit (see ‘Baseline Visit 12709A rollover’ column). The Informed Assent/Consent Form must be signed before any study-related activities take place.
- b Applicable only for *De novo* patients.
- c Applicable only for 12709A rollover patients. Assessments marked with (✓) in this column will be used from 12709A study and therefore not repeated.
- d This visit should take place as soon as possible after the patient withdraws from the study. Any visit during the open-label treatment period can be converted into a Withdrawal Visit on the day of the visit.
- e Applicable for patients withdrawn prior or at Visit 8: Safety follow-up should be scheduled approximately 30 days after the last dose of IMP. It can be a telephone contact, unless an SAE has occurred since the last visit or unless there was a clinically significant abnormal safety laboratory test value at the last visit. In such cases, safety follow-up(s) must be scheduled to allow for a medical examination and/or blood sampling. Further safety follow-up visits beyond 30 days may be needed as judged by the investigator (if further safety follow-up visits are performed, these must be recorded in the patient’s medical record, and not in the eCRF).

- f If the date of a visit does not conform to the schedule, subsequent visits should be planned to maintain the visit schedule relative to the Baseline Visit. Consider that the number of days between 2 visits must not exceed the number of days for which the patient has been dispensed IMP.
- g The data from the Screening Visit in the Study 12709A eCRF will be used.
- h The K-SADS-PL will be used to confirm diagnosis of MDD and to assess possible psychiatric co-morbidities.

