8.4 Randomization Visit (Visit 8)

The double-blind period starts with the Randomization Visit (8) at Week 12. Patients who fulfil the randomization criteria (section 5.4) will be randomly assigned via a centralized randomization system to receive vortioxetine or placebo in a 1:1 ratio.

Patients rolling over from Study 12712A need to fulfil inclusion/exclusion criteria detailed in sections 5.3. At the Randomization Visit, *de novo* patients and rollover patients from Study 12709A undergo evaluation of randomization criteria, and evaluation of efficacy and safety assessments as per [Panel 3](#). Patients who do not meet the randomization criteria will be withdrawn from the study and complete an early withdrawal visit.

For 12712A-patients, last available values from assessments and procedures (efficacy/safety, and use of concomitant medication) performed at either Visit 7 (Week 8) and/or Visit 8 (Week 10), or Visit 9 (Week 12) in Study 12712A will be the Randomization Visit values for this study. For patients who rollover at Visit 7 or Visit 8, weight, height, Tanner staging, menstrual cycle, and examinations should be done at the Randomization Visits (detailed in [Panel 3](#) and section 11.1.2).

The schedule of assessments during the Double-blind Period is described in [Panel 3](#).

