16.1.3 Covid-19 impact

This study has been carried out during the pandemic of COVID-19. As a result, impact on assessments and the timing of assessments is expected. Data will be collected to evaluate the impact of COVID-19 on the conduct of the study. These data will be presented in listings and summarized if needed.

Missing visits:

Depending on the impact of COVID-19 on data collection, it will be decided whether data from missing visits due to COVID-19 will be imputed using the LOCF approach as well.

Remote visits:

Scheduled and unscheduled visits are allowed to take place remotely via voice call or voice and video call. All the data from scheduled visits recorded remotely will be included in the analysis at the designated visit. Visit windowing as explained in [Panel 6](#) above will be applied to remote visits.

A listing will be presented on the details of remote visits including which visit was conducted remotely, date of remote visit, and whether or not patient reported outcomes and clinician reported outcomes were assessed during the remote visit.

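### SAP Panel 6 maps open-label Visit 8 only to Day 86 although Day 87 is permitted, so a Week 12 value taken at a Day 87 Withdrawal Visit can drop out of the open-label Week 12 tables

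*SAP*

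**What the plan says.** Panel 6 in SAP 16.1.1 gives each visit two ranges of days. The time window is when the visit may take place. The mapping window decides which visit an assessment counts towards in the analysis.

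- The open-label Week 12 row reads "V8(end of Open Label Period) 12 NA 84 81 to 87 78 to 86". The last three entries are the nominal day, the time window and the mapping window.
- The next open-label row, Safety Follow-up for children who do not enter the double-blind period, ends "112 110 to 114 >86".
- The double-blind block repeats the Visit 8 ranges and continues with "V9 13 1 91 88 to 93 87 to 95".

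The text above the panel treats two kinds of visit differently. For scheduled visits: "The assessments at the scheduled visits will be used for the analyses". For Withdrawal Visits: "The assessment at the Withdrawal Visit for patients withdrawn from study will be assigned to a nominal visit in the Treatment Period", by way of Panel 6. If both kinds land on the same visit, the Withdrawal Visit value is used. SAP 16.1.3 adds that Panel 6 windowing "will be applied to remote visits", but it also says that remote data from scheduled visits are analysed at their designated visit.

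Protocol 8.4 says of Week 12: "Patients who do not meet the randomization criteria will be withdrawn from the study and complete an early withdrawal visit". Footnote d to Protocol Panel 2 says: "Any visit during the open-label treatment period can be converted into a Withdrawal Visit on the day of the visit".

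**The concern.** Day 87 is a permitted day for Visit 8 but lies outside that visit's own mapping window. A Withdrawal Visit on that day is sent by the panel to Safety Follow-up. SAP 4.2 defines Safety Follow-up as a separate period, whereas the text requires a visit in the Treatment Period. A programmer has to break one rule or the other.

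What is at stake is the open-label Week 12 column: the CDRS-R descriptive table by inclusion source (SAP 11.1) and the by-visit safety tables (SAP 12.2). SAP Appendix II schedules no CDRS-R or laboratory tests at Safety Follow-up, so a value sent there has no natural row. LOCF is specified for the double-blind period only (SAP section 16), so nothing fills the gap. Failing the response criteria is the protocol's own reason for withdrawal at this visit, so the children affected would tend to have higher CDRS-R scores than those who stay in the table.

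**Working it through.** **1. Reproduce the time window.** Nominal day ± visit window (Protocol Panel 2): 84 ± 3 = 81 to 87. This agrees with Panel 6.

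**2. Does each open-label mapping window contain its time window?**

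| Visit | Time window | Mapping window | Contained? |
|---|---|---|---|
| V3 | 4–10 | 1–10 | yes |
| V4 | 11–17 | 11–21 | yes |
| V5 | 25–31 | 22–42 | yes |
| V6 | 53–59 | 43–63 | yes |
| V7 | 67–73 | 64–77 | yes |
| V8 | 81–87 | 78–86 | **no, Day 87 is outside** |

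**3. Is Day 86 deliberate?** The mapping limits follow the midpoint between adjacent nominal days, rounded down. For V7/V8, (70 + 84)/2 = 77, as stated. The rule reproduces the upper limit of every main row from V3 to V17 except two:
- V8/V9: (84 + 91)/2 = 87.5, so V8 should end on Day 87; the panel says 86.
- V9/V10: (91 + 98)/2 = 94.5, so V9 should end on Day 94; the panel says 95.

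Measured against the open-label Safety Follow-up row instead, the midpoint is (84 + 112)/2 = 98. Neither comparison gives 86.

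**4. Route the permitted days.** Days 81 to 86 go to V8. Day 87 goes to Safety Follow-up in the open-label block and to V9 in the double-blind block. So 1 of 7 permitted days is misdirected.

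**5. What happens on Day 87.**
- The child fails the criteria and Visit 8 is recorded only as a Withdrawal Visit: the panel moves the value out of Week 12.
- The child fails and Visit 8 is recorded as the scheduled visit: the value stays at Week 12.
- The child is randomized: the value stays at Week 12 as a scheduled assessment. If the visit was remote, the two statements in SAP 16.1.3 leave it open whether the value stays or moves to V9.

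**6. How many children?** The documents give neither the spread of visit days nor the number leaving at Visit 8. Purely as assumptions, take 20 to 60 failures at Week 12 and 5% to 25% of them seen on Day 87:
- at 5%: 20 × 0.05 = 1 to 60 × 0.05 = 3
- at 1/7 (uniform over the window): 20/7 = 2.9 to 60/7 = 8.6
- at 25%: 20 × 0.25 = 5 to 60 × 0.25 = 15

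Each figure must then be multiplied by the share of these visits recorded solely as Withdrawal Visits. That share is also unknown and may be zero.

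**7. Other cells in the same panel.** Two more affect mapping:
- V10 is permitted from Day 95 (98 − 3) but mapped from Day 96, so Day 95 falls in V9.
- V17 mapping ends at Day 280 and V18 is above 281, so Day 281 has no visit.

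Two are in the time-window column only and do not drive assignment:
- V9 shows 88 to 93, but 91 ± 3 = 88 to 94.
- Open-label follow-up shows 110 to 114, but 112 ± 5 = 107 to 117.

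**The case against.** The best defence is that the text already protects these values. Scheduled assessments are used as scheduled, and Visit 8 is a scheduled visit with its own CDRS-R. Conversion to a Withdrawal Visit is allowed, not required. The text also confines Withdrawal Visit values to the Treatment Period, so Safety Follow-up should not be an eligible target. This stands in part: the loss is conditional, and at the least the panel and the text conflict. It does not remove the problem, because conversion is an ordinary route for a child who fails at Week 12 and the panel then gives a definite wrong answer.

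A reader might infer that only non-responders are lost. The documents do not support that. A responder withdrawn on Day 87 for another reason is treated identically, and a randomized child seen remotely that day might move too. Children who fail at Week 10 are also to be withdrawn (SAP 3.1), so the Week 12 table is already selected whatever the mapping.

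A reader might also put a figure on the bias. With 80 randomized children at a mean CDRS-R of 26, 30 to 60 failures at 40 to 50, and one seventh of the failures dropped, the Week 12 mean falls by about 0.4 to 0.9 points. None of these means or counts of failures is in the documents. The calculation also gives an open-label Week 12 value to all 80 randomized children, although those rolling over from Study 12712A enter at randomization and have none in this study.

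Finally, safety information is not lost overall. SAP 12.2 also summarizes the last assessment and any post-baseline PCS value from all available assessments. Only by-visit rows can change.

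**Conclusion.** The boundary is wrong as written, and the panel conflicts with the text it serves. The consequence is minor. On one of seven permitted days, a Week 12 value can leave the open-label by-visit tables if Visit 8 is recorded solely as a Withdrawal Visit. That would fall mainly on children who did not respond and would tend to make the Week 12 summary look somewhat better.

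The size cannot be derived from the documents; the counts in the working are illustrations only. The tables concerned are descriptive. The primary analysis uses the date of relapse (SAP 11.3.1), and the randomization decision uses the scores themselves (Protocol 5.4), so neither depends on this mapping.

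**What to change.** In Panel 6:

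- Extend the open-label V8 mapping to at least Day 87, with Safety Follow-up starting the day after. Day 87 is enough to cover the permitted window. Day 98 is the midpoint to follow-up, but under the SAP's tie rule it would let a separate later Withdrawal Visit replace the scheduled Week 12 value, so that choice should be deliberate.
- Move the double-blind V8/V9 boundary to match: V8 to Day 87, V9 from Day 88.
- Move the V9/V10 boundary: V9 to Day 94, V10 from Day 95.
- Assign Day 281 to V17 or V18.
- As tidying only, correct the time windows for V9 (88 to 94) and open-label follow-up (107 to 117).

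In the text of 16.1.1, state that a Visit 8 converted to a Withdrawal Visit is analysed as Week 12. In 16.1.3, say whether a remote scheduled visit keeps its designated visit or is re-mapped.

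The cost is a few table cells and two sentences in the SAP, made before the blind is broken. No extra data are needed.

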8.5 Withdrawal Visit

Open-label Period: Patients who withdraw from the study prior to Visit 8 will be asked to attend a Withdrawal Visit, if at all possible. The visit must be scheduled as soon as possible after withdrawal. Patients who withdraw from treatment will also be asked to attend a Safety Follow-up Visit.

Patients who do not fulfil randomization criteria for remission or adequate response at Week 10 and/or Week 12 will be withdrawn from the study and will complete an early Withdrawal Visit.

Double-blind Period: Patients who withdraw from the study prior to the Completion Visit after 26 weeks of treatment in the double-blind period will be asked to attend a Withdrawal Visit, if at all possible. The visit must be scheduled as soon as possible after withdrawal. Patients who withdraw from the study will also be asked to attend a Withdrawal Visit (Visit 17, where both efficacy and safety are assessed).

No new information will be collected from patients who withdraw from the study, except information collected in relation to the scheduled Withdrawal Visit or needed for the follow-up of adverse events (section 10.5).

The reason for withdrawal must be recorded in the eCRF.

For a patient and/or the patient's parent(s)/legal representative(s) who withdraw consent:

- if the patient and/or the patient's parent(s)/legal representative(s) withdraw consent during a visit and then agree(s) to it being the final visit, the investigator will complete the visit as a Withdrawal Visit and all the data collected up to and including that visit will be used
- if the patient and/or the patient's parent(s)/legal representative(s) withdraw(s) consent during a telephone conversation, the investigator will ask the patient if he or she will attend a Withdrawal Visit. If the patient:
 - agrees to attend a Withdrawal Visit, all the data collected up to and including that visit will be used
 - refuses to attend a Withdrawal Visit, the investigator should attempt to follow the patient's safety and future treatment; any information collected will only be recorded in the patient's medical records
- if the patient and/or the patient's patients/legal representative explicitly request(s) that the patient's data collected from the time of withdrawal of consent onwards not be used, this will be respected

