4.2 Definition of Periods

The following periods can be identified:

Screening period

A Screening Visit will be performed only for de novo patients. Patients rolling over from Study 12709A will proceed directly to the Baseline Visit. Therefore, the screening period is not applicable for these patients. In addition, this period is not applicable for patients rolling over from Study 12712A, as these patients will enrol the study at the randomization visit. The screening period begins when the first screening assessment is done after written Informed Assent/Consent has been obtained, and ends at the Baseline Visit for the Open Label Period (visit 2).

Open Label Period

De novo patients who continue to meet all inclusion criteria and none of the exclusion criteria (see section 5.3 of the study protocol) will be enrolled into a 12-week Open Label Period. For patients rolling over from Study 12709A, the Baseline Visit of the Open Label Period will be performed the same day as the Week 12 (Completion) Visit of Study 12709A.

Patients eligible for entering the Open Label Period will start IMP (vortioxetine) at the Baseline Visit of the Open Label Period.

The duration of the Open Label Period is 12 weeks or until the patient is withdrawn from the study, whichever comes first. If a patient withdraws from the study, the Open Label Period ends at the withdrawal visit.

Double-Blind Treatment Period

The Double-Blind Treatment Period starts at the randomization visit (visit 8) and ends after 26 weeks of treatment (visit 17), or until the patient will be withdrawn from the study, whichever comes first. If a patient withdraws from the study the Double-Blind Treatment Period ends at the withdrawal visit.

Patients rolling over from Study 12712A will have their first visit in this study at visit 8 (the Randomization Visit). For 12712A-patients the last available values from assessments and procedures (efficacy/safety, and use of concomitant medication) performed at either Visit 7 (Week 8) and/or Visit 8 (Week 10), or Visit 9 (Week 12) in Study 12712A will be the Randomization Visit values for this study.

Safety Follow-up Period

The Safety Follow-up Period has a duration of 4 weeks after the last IMP intake. This period starts at the date of last IMP intake.

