11.4 Analysis Methodology for the Secondary Endpoints

11.4.1 Analysis of the Secondary Endpoint(s)

Relapse

The number of relapses will be summarized per visit, per treatment group and overall. The relapse criteria as defined in section 11.3 will be used.

The relapse over the 26 weeks Double-Blind Treatment Period will be analysed using logistic regression, with treatment and inclusion source as fixed factors and CDRS-R Total Score at randomization as covariate. In addition, the analysis will be repeated using the LOCF (Last Observation Carried Forward) approach for missing data.

The odds ratio estimates with 95% confidence intervals will be presented. The odds ratio and the confidence limits will be based on the profile likelihood.

Secondary efficacy variables (CDRS-R total score, PQ-LES-Q scores (total score and overall score), CGI-S and CGI-I) will be analysed on an exploratory basis over the 26-week Double-Blind Treatment Period by Mixed Model Repeated Measurements (MMRM) and analysis of covariance (ANCOVA).

For the purpose of the analysis the change from randomization in CDRS-R total score, PQ-LES-Q scores, and in CGI-S score will be computed.

For both the MMRM and the ANCOVA, the dependent variable will be the change from randomization in CDRS-R total score, change from randomization in PQ-LES-Q scores, change from Randomization in CGI-S score and the absolute CGI-I score, respectively.

The MMRM will have treatment, week and inclusion source as fixed factors and the randomization score will be added as a covariate. For CGI-I, the score at randomization for the CGI-S will be used as covariate.

In addition, the interaction between treatment and week and between randomization score and week will be included and an unstructured covariance matrix will be applied. The Kenward-Roger approximation will be used to estimate denominator degrees of freedom.

In the ANCOVA treatment and inclusion source will be included as fixed factors and the respective randomization score will be included as a covariate. For CGI-I, the score at randomization for the CGI-S will be used as covariate.

Only the observed cases (OC) approach will be used.

Paediatric Quality of Life Enjoyment and Satisfaction Questionnaire

The PQ-LES-Q consist of 15 items, item 1 to 14 assess the degree of satisfaction experienced by patients in various areas of daily functioning and item 15 allows patients to summarize their experience in a global rating.

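### Panel 6 of the SAP maps some CGI-I and PQ-LES-Q Withdrawal Visit scores to visits where the scale is not scheduled, and the SAP does not say what the observed-cases MMRM does with them

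*SAP*

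**What the plan says.** SAP 16.1.1 gives the rule for exits: "The assessment at the Withdrawal Visit for patients withdrawn from study will be assigned to a nominal visit in the Treatment Period", using the mapping windows in Panel 6. Protocol 8.5 asks patients who leave the double-blind period to "attend a Withdrawal Visit (Visit 17, where both efficacy and safety are assessed"), and the double-blind schedule has both CGI-I and PQ-LES-Q at Visit 17. Relapsers must be withdrawn (SAP 3.2), so an exit score is expected for each of them.

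After randomization, SAP Appendix II schedules CGI-I at V9, V11, V13, V15 and V17, and PQ-LES-Q at V11, V13, V15 and V17. Panel 6 has three starred rows for these scales: V11 for CGI-I alone (Days 101-133), V13 for both (134-182), and "V15, CGI-I and PQ-LES-Q only" (183-238). The footnote gives the reason: "Different mapping for these variables only, due to a different schedule of assessments". All other days fall to the general rows.

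SAP 11.4.1 analyses both scales by an MMRM with week as a factor and treatment-by-week and score-by-week interactions; "an unstructured covariance matrix will be applied". On missing data it says: "Only the observed cases (OC) approach will be used". Neither 11.4.1 nor Appendix III lists the weeks that enter the model for each scale. Section 16 describes LOCF for these scales: "The last usable assessment in the Double-Blind Treatment Period (excluding the randomization assessment) will be used to impute missing values for the LOCF".

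**The concern.** The starred rows exist so that an exit score lands on a visit where the scale is scheduled. They do this for only part of the period. Elsewhere the general rows send the score to a visit at which no continuing patient has a value, and the SAP does not say what happens next.

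There are two readings. If such scores are left out, a relapser who exits at V9 or V10 has no post-randomization PQ-LES-Q in the MMRM, and the worsening at relapse is lost. If they are kept, the model gains week levels filled almost only by withdrawals, and many covariances in the unstructured matrix have no data behind them. Two programmers could therefore produce different analyses from the same SAP.

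**Working it through.** **Step 1. Map every day.** Inputs: Panel 6 mapping windows (starred row where one exists, otherwise the general row) and the Appendix II schedule.

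| Exit day | CGI-I goes to | Scheduled? | PQ-LES-Q goes to | Scheduled? |
|---|---|---|---|---|
| 87-95 | V9 | yes | V9 | **no** |
| 96-100 | V10 | **no** | V10 | **no** |
| 101-105 | V11 | yes | V10 | **no** |
| 106-119 | V11 | yes | V11 | yes |
| 120-133 | V11 | yes | V12 | **no** |
| 134-182 | V13 | yes | V13 | yes |
| 183-238 | V15 | yes | V15 | yes |
| 239-252 | V16 | **no** | V16 | **no** |
| 253-280 | V17 | yes | V17 | yes |

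Unscheduled days: CGI-I 5 + 14 = 19 of 194 (9.8%); PQ-LES-Q 9 + 10 + 14 + 14 = 47 of 194 (24.2%).

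**Step 2. Check the panel's own logic.** Midpoints between scheduled visits: V11/V13 (112 + 154)/2 = 133; V13/V15 (154 + 210)/2 = 182; V15/V17 (210 + 266)/2 = 238. These are the starred upper limits. A V15 window ending at 238 implies a V17 window starting at 239, but V17 starts at 253. The V9/V11 midpoint is (91 + 112)/2 = 101.5, consistent with the starred CGI-I V11 start at 101, yet the V9 window ends at 95.

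**Step 3. Expected number of affected scores.** Inputs: cumulative relapse 0.42 and 0.69 over 26 weeks and 40 per arm (SAP section 14). Assumptions: constant hazards, randomization on Day 84, no other dropout, every relapser gives an exit score.

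Hazards per day are -ln(0.58)/182 = 0.00299 (vortioxetine) and -ln(0.31)/182 = 0.00644 (placebo). Their ratio is 2.15, which reproduces the plan's hazard ratio. Expected relapsers: 40 × 0.42 + 40 × 0.69 = 16.8 + 27.6 = 44.4. Relapses first seen at a visit: 40 × [exp(-λ × days to previous visit) - exp(-λ × days to this visit)].

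| Visit | Vortioxetine | Placebo |
|---|---|---|
| V9 | 0.83 | 1.76 |
| V10 | 0.81 | 1.68 |
| V12 | 1.51 | 2.88 |
| V16 | 2.21 | 2.93 |

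PQ-LES-Q:
- Exits on nominal days (V9, V10, V12): 3.15 + 6.32 = 9.5 of 44.4 (21%). By arm: 3.2 of 16.8 (19%) and 6.3 of 27.6 (23%).
- Exits uniform over the ±3 or ±5 day visit windows: add V16 × 5/11 (Days 239-243 of 233-243), that is 9.47 + 5.14 × 5/11 = 11.8 (27%).
- Exits in continuous time: 13.3 (30%).
- Nominal days, with no relapse recorded at V9 or V10: V12 only, 4.4 (10%).

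CGI-I:
- Nominal days (V10): 2.5 (6%).
- Uniform over windows: 2.50 × 5/7 + 5.14 × 5/11 = 4.1 (9%). Continuous time: 4.1 (9%).
- V10 on its nominal day, V16 spread over its window: 2.50 + 2.34 = 4.8 (11%).
- Nominal days, with no relapse recorded at V9 or V10: 0.

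**Step 4. The unstructured matrix if the scores are kept.** A withdrawal score is the patient's last, so an exit-only week can pair only with earlier scheduled weeks.

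- PQ-LES-Q: Weeks 1, 2, 4, 6, 10, 18, 22 and 26, with 1, 2, 6 and 22 exit-only. Pairs with data: 6 among scheduled weeks, plus (4,6), (4,22), (10,22) and (18,22), so 10 of 28; **18 are empty**. Covariance parameters rise from 10 to 36.
- CGI-I: Weeks 1, 2, 4, 10, 18, 22 and 26, with 2 and 22 exit-only. Pairs with data: 10 among scheduled weeks, plus (1,2) and four with Week 22, so 15 of 21; **6 are empty**. Parameters rise from 15 to 28.

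**The case against.** The strongest reply concerns weight. Both scales are analysed on an exploratory basis and the protocol has no testing strategy, so no confirmatory claim depends on them. The affected shares are similar by arm, and no shift in the Week 26 contrast has been shown; most relapsers have no Week 26 value in any case. Not every relapser will attend a Withdrawal Visit. The CDRS-R relapse criterion requires two weeks of worsening, so relapses at V9 are uncertain. All of this stands, and it is why the point is limited and the counts are given as a range.

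A second reply is that SAP 16.1.1 opens by saying that scheduled-visit assessments are analysed, so a sensible analyst would fit only the scheduled weeks and the matrix problem would not arise. That is the more natural reading, but the SAP does not state it, and under it the exit scores are lost. LOCF in section 16 does not recover them, because 11.4.1 restricts these models to observed cases.

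A third reply is that starting V17 at Day 239 moves some Week 22 exits, mostly relapsers, into the endpoint week. This is correct and is a real cost of that option.

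On day origin, "Patients rolling over from Study 12712A will have their first visit in this study at visit 8 (the Randomization Visit"), and they have no open-label baseline here. Panel 6 labels V8 as Day 84 and Week 0 from randomization, which largely implies the anchor. This part is minor.

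**Conclusion.** The concern holds. Panel 6 departs from its own midpoint rule at V9 (CGI-I), V11 (PQ-LES-Q) and V17 (both), and nothing in 11.4.1, section 16 or Appendix III repairs it. Under the plan's relapse rates and the assumptions above, about a fifth to a quarter of relapsers' PQ-LES-Q exit scores are affected (range 10% to 30%), and 0% to 11% for CGI-I. The singular-matrix consequence is conditional on keeping the unscheduled weeks; otherwise the consequence is loss of exit scores. No direction of bias is claimed. It should be corrected before unblinding, but the consequences are confined to two secondary scales; the primary Cox analysis, CDRS-R and CGI-S are unaffected.

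**What to change.** Make the Panel 6 windows contiguous for each scale, for example:

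- CGI-I: V9 87-100, V11 101-133, V13 134-182, V15 183-238, V17 239-280.
- PQ-LES-Q: V11 87-133, V13 134-182, V15 183-238, V17 239-280.

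If the sponsor prefers not to widen V11 or V17, state in 11.4.1 that scores mapped to unscheduled weeks are left out of the MMRM and used only in the LOCF descriptive statistics. In either case, add one line that double-blind days are counted from the randomization date (Visit 8 = Day 84) for all patients, including 12712A rollovers.

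The cost is a table edit, a sentence and the mapping program. The downside of widening is that some exit scores move to a visit up to about four weeks away (Day 239 to Week 26), as the existing wide windows already allow. With V16 exits spread over their window, about 2.3 would enter Week 26 (5.14 × 5/11), while those up to Day 238 go to Week 18. The sponsor should accept that change to the endpoint week knowingly or choose the one-sentence alternative.
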